9.2.4 Tertiary/exploratory endpoint analyses

Statistical analysis for exploratory endpoints will be described in the SAP.

9.2.5 Multiplicity adjustment

Both co-primary endpoints will need to achieve non-inferiority as specified in [Section 9.2.2](#), in order to claim the non-inferiority of ISA SC+ PomDex relative to Isa IV + PomDex.

Hypothesis testing of key secondary endpoints (VGPR or better rate per IRC assessment and CT4W) for non-inferiority, and key secondary endpoints (incidence of IRs and percentage of participants satisfied or very satisfied based on the PESQ questionnaire) for superiority will be carried out. A hierarchical test procedure will be used to control the familywise Type I error rate at one-sided significance level of 0.025 meaning that testing of key secondary endpoints will be performed only if the non-inferiority for both co-primary endpoints are established and testing on subsequent endpoints will continue only if the null hypothesis for the previously tested endpoint is rejected. The hierarchical procedure for testing the key secondary endpoints comparing SC arm with IV arm will be performed according to the following order:

- VGPR or better rate for non-inferiority.
- CT4W for non-inferiority.
- Incidence of IRs for superiority.
- Percentage of participants who reported satisfied or very satisfied with the injection method used to administer the study medication at C5D15 visit for superiority.

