If the co-primary endpoints are significant, the key secondary endpoints will be tested by hierarchical testing in the order of VGPR or better rate, CT4W, incidence rate of IRs, and the percentage of participants who reported satisfied or very satisfied with the injection method used to administer the study medication.

VGPR or better rate per IRC will be summarized for the ITT population in the same way as for ORR endpoint. The non-inferiority test for non-unity null according to Farrington and Manning (1990) will be performed for VGPR or better rate. The non-inferiority margin is 0.6312 which was calculated as 40% retention of the observed historical clinical benefit of VGPR or better ratio 0.478 (upper bound of the 95% CI of rate ratio for Pd over CD38+ Pd as demonstrated in ICARIA-MM trial) under the logarithm scale then converting back to its original scale. If the lower bound of the 95% CI is not less than a non-inferiority margin of 0.6312, the non-inferiority of Isa-SC + Pd relative to Isa- IV + Pd on the VGPR or better rate will be concluded.

The PK endpoint of CT4W will be summarized for the PP-PK population for CT4W in the same way as for the C_{trough} at steady state endpoint. The non-inferiority of Isa- SC + Pd relative to Isa-IV + Pd on CT4W will be concluded if the lower bound of the 90% CI for the geometric mean ratio of CT4W is at least 80% (a non-inferiority margin of 80%).

Incidence rate of IRs will be compared between treatment arms on the safety population using the Fisher's exact test. The relative risk, odds ratio of ISA- SC+ Pd relative to Isa- IV + Pd with their 95% CI will be provided.

Percentage of participants who reported satisfied or very satisfied with the injection method used to administer the study medication based on the PESQ at C5D15 visit will be compared between treatment arms on the ITT population using the stratified Cochran–Mantel–Haenszel (CMH) method.

Analysis of other secondary endpoints

The median PFS per IRC assessment and probabilities of being progression free at different time points calculated using the Kaplan-Meier methods as well as corresponding 95% CI will be presented by treatment arm. The Kaplan-Meier PFS curves will also be provided. The Hazard Ratio (HR) estimated from the Cox proportional hazards model as well as its associated 95% CI will be provided too.

The analysis for PFS2, OS, DOR, and time-to-response (TTR) will be similar to that described for PFS per IRC assessment.

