9.2.2 Primary endpoint(s) analyses

The number and proportion of participants who achieve ORR per IRC assessment will be calculated for each group. The relative risk of Isa-SC + Pd relative to Isa-IV + Pd and its two-sided 95% CI using Farrington and Manning method will be provided. If the lower bound of the 95% CI is not less than a non-inferiority margin of 0.839, the non-inferiority of efficacy Isa- SC + Pd relative to Isa- IV + Pd will be concluded. The odds ratio of ISA- SC+ Pd relative to Isa- IV + Pd with their 95% CI will also be provided.

For the co-primary PK endpoint of C_{trough} at steady state (corresponding to predose at C6D1), summary statistics such as geometric means, coefficient of variation, median and range will be provided for treatment group. The ratio of the geometric means of Isa-SC+ Pd relative to Isa- IV + Pd and corresponding two-sided 90% CI will be provided by calculating the 90% CI under the logarithm scale then converting back to its original scale. The non-inferiority of PK Isa- SC + Pd relative to Isa- IV + Pd will be concluded if the lower bound of the 90% CI for the geometric mean ratio of C_{trough} at steady state is at least 80% (a non-inferiority margin of 80%).

The non-inferiority of ISA- SC+ Pd relative to Isa- IV + Pd will be concluded if both the efficacy and PK endpoints achieve non-inferiority.

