9.2.3 Secondary endpoint(s) analyses

9.2.3.1 Key Secondary Endpoints

VGPR or better rate per IRC assessment will be summarized for the ITT population in the same way as for ORR endpoint. The non-inferiority test for non-unity null according to Farrington and Manning (1990) will be performed for VGPR or better rate. The non-inferiority margin is 0.6312 which was calculated as 40% retention of the observed historical clinical benefit of VGPR or better ratio 0.478 (upper bound of the 95% CI of rate ratio for Pd over CD38+ Pd as demonstrated in ICARIA-MM trial) under the logarithm scale then converting back to its original scale. If the lower bound of the 95% CI is not less than a non-inferiority margin of 0.6312, the non-inferiority of Isa-SC + Pd relative to Isa- IV + Pd on the VGPR or better rate will be concluded.

The PK endpoint of CT4W will be summarized for the CT4W-PK population in the same way as for the C_{trough} at steady state endpoint. The non-inferiority of Isa- SC + Pd relative to Isa-IV + Pd on CT4W corresponding to predose at C2D1 will be concluded if the lower bound of the 90% CI for the geometric mean ratio of CT4W is at least 80% (a non-inferiority margin of 80%).

Incidence rate of IRs will be compared between treatment arms on the safety population using the Fisher's exact test. The relative risk, odds ratio of ISA- SC+ Pd relative to Isa- IV + Pd with their 95% CI will be provided.

Percentage of participants who reported satisfied or very satisfied with the injection method used to administer the study medication based on the PESQ questionnaire at C5D15 visit will be compared between treatment arms on the ITT population using the stratified CMH method.

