9.5 SAMPLE SIZE DETERMINATION

A total sample size of 534 participants (randomization ratio 1:1, ie, 267 randomized participants in the SC arm, and 267 randomized participants in the IV arm) was determined to demonstrate non-inferiority of SC arm versus IV arm on the proportion ratio of participants who achieved ORR, and the geometric mean ratio of C_{trough} at steady state (corresponding to predose at C6D1). For the co-primary efficacy endpoint of ORR, the non-inferiority test for non-unity null according to Farrington and Manning (1990) was implemented. With 2.5% one sided Type I error rate, and a non-inferiority margin of 0.839 which was calculated as 40% retention of the observed historical clinical benefit of ORR ratio 0.7463 (upper bound of the 95% CI of rate ratio for Pd over CD38+Pd as demonstrated in ICARIA-MM trial) under the logarithm scale then converting back to its original scale, 534 randomized participants provide approximately 80% power for this

efficacy co-primary endpoint assuming that ORR for IV arm is 60.4% and the true response rate ratio is 1.02 for SC arm over IV arm. For the PK co-primary endpoint of C_{trough} at steady state, assuming C_{trough} at steady state follows log normal distribution with a true geometric mean ratio of 1 and a CV of 75%, and an assumed drop-out rate of no more than 50% to the PK per-protocol population, 534 randomized participants will provide at least an 86% power to show the lower bound of the 90% CI of the geometric mean ratio of C_{trough} at steady state is at least 80% (a non-inferiority margin of 80%).

Calculations were made based on SAS 9.4 ([1](#)).

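### Section 9.2.5 claims familywise control at one-sided 0.025, but both PK steps are tested at one-sided 0.05, so the whole sequence is controlled only at 0.05

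*Protocol*

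**What the plan says.** Protocol section 9.2.5 sets out one procedure: "A hierarchical test procedure will be used to control the familywise Type I error rate at one-sided significance level of 0.025". The entry condition is that "testing of key secondary endpoints will be performed only if the non-inferiority for both co-primary endpoints are established", and after that "testing on subsequent endpoints will continue only if the null hypothesis for the previously tested endpoint is rejected". The order is VGPR or better rate, CT4W, incidence of infusion reactions, then satisfaction with the injection method.

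The decision rules are given elsewhere:

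- **ORR (9.2.2) and VGPR or better (9.2.3.1):** lower limit of the 95% CI against margins of 0.839 and 0.6312.
- **C6D1 trough (9.2.2):** PK non-inferiority "will be concluded if the lower bound of the 90% CI for the geometric mean ratio of" the trough is at least 80%, using a two-sided 90% interval.
- **CT4W (9.2.3.1):** non-inferiority is concluded "if the lower bound of the 90% CI for the geometric mean ratio of CT4W is at least 80" per cent. The synopsis agrees: "on CT4W will be concluded if the lower bound of the 90% CI for the geometric mean ratio of CT4W" meets the same limit.

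Section 9.5 keeps the two kinds of test apart. For ORR it says "With 2.5% one sided Type I error rate, and a non-inferiority margin of 0.839". For PK it gives no alpha and says "534 randomized participants will provide at least an 86% power to show the lower bound of the 90% CI".

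**The concern.** A lower limit taken from a two-sided 90% interval is a one-sided test at 0.05. Section 9.2.5 promises 0.025 over a family that names CT4W as a member and is gated by the C6D1 trough, yet both are tested at twice that level. The plainest conflict is at CT4W, which sits inside the ordered list. The C6D1 trough is part of the gate, so it carries the same level into the overall claim. No section of the protocol reconciles the two levels.

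Familywise control is a central property of a confirmatory protocol. If the statement stands, the trial will claim a strength of control that its rules do not give. The shortfall falls on the two PK non-inferiority claims and on the overall SC-versus-IV conclusion.

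**Working it through.** **1. Which level do the protocol's own power figures imply?**

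PK inputs from 9.5: CV 75%, true ratio 1, margin 0.80, 534 randomized, 50% drop-out. That leaves 133 to 134 evaluable per arm.

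- Log-scale SD: σ = √ln(1 + 0.75²) = 0.668.
- Distance to the margin: −ln 0.80 = 0.2231.
- Standard error at 133 per arm: 0.668 × √(2/133) = 0.0819, so the noncentrality is 0.2231 / 0.0819 = 2.72.

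| Evaluable per arm | Power, one-sided 0.05 | Power, one-sided 0.025 |
|---|---|---|
| 133 | 85.8% | 77.5% |
| 134 | 86.0% | 77.8% |

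(Noncentral t. The normal approximation gives 86.0–86.2% and 77.8–78.1%.) The stated 86% reproduces only at one-sided 0.05.

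ORR inputs from 9.5: IV rate 60.4%, ratio 1.02, margin 0.839, 267 per arm, one-sided 0.025. With the Farrington-Manning test, the SC rate is 1.02 × 0.604 = 0.6161 and the contrast is 0.6161 − 0.839 × 0.604 = 0.1093. The standard errors are 0.0390 under the null and 0.0389 under the alternative. Power = Φ[(0.1093 − 1.96 × 0.0390) / 0.0389] = 80.0%, as stated.

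The mixed levels are therefore built into the sample size. The 90% interval is not a slip.

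**2. The familywise bound.**

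The one-sided levels in order are ORR 0.025, C6D1 trough 0.05, VGPR 0.025, CT4W 0.05, infusion reactions 0.025 and satisfaction 0.025. Section 9.2.3.1 gives no level for the last two; 0.025 is taken from 9.2.5, and the result does not depend on it.

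In a fixed sequence, a false claim requires rejecting the first true null, so the error is at most that test's level. Requiring both co-primaries to succeed prevents the levels from adding up, but it does not lower the larger one. The bound is the maximum, 0.05.

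A simulation (2,000,000 runs per configuration, power near 1 for every non-null test) gave 0.050 with only the C6D1 trough at its margin, 0.050 with only CT4W at its margin, and 0.025 with only one of the other four null. With both PK nulls true it remained 0.050.

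**3. Size under the planning assumptions.**

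- *True C6D1 ratio 0.80, overall claim.* 0.05 × 0.800 = 4.0% at an ORR ratio of 1.02. If the ORR ratio is 1.10, ORR power is 98.4% and the figure is 0.05 × 0.984 = 4.9%. Independence assumed.
- *True CT4W ratio 0.80.* This needs VGPR power, which the protocol does not give. Assuming the 31.8% rate reported for the isatuximab arm of ICARIA-MM (2.2.3.1), ratio 1.00, margin 0.6312 and 267 per arm, the contrast is 0.318 × (1 − 0.6312) = 0.1173. Power = Φ[(0.1173 − 1.96 × 0.0322) / 0.0337] = 94.6%. Under independence the error is 0.05 × 0.80 × 0.858 × 0.946 = 3.2%. For an IV rate of 30–40%, power is 92.9–98.9% and the error 3.2–3.4%.
- *Correlation between the PK statistics.* With a correlation of 0.5 to 0.9 (assumed) and the other tests independent, the CT4W figure rises to about 3.8%. The limit is 0.05 × 0.80 × 0.946 = 3.8%, because passing CT4W then almost implies passing C6D1.

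**The case against.** The strongest case is that nothing operational is unclear. The PK criterion is a 90% lower limit of at least 80% wherever it is stated, and ORR and VGPR use the 95% limit throughout. Two analysts would run the same six tests and reach the same conclusions. A 90% interval is usual for PK and was fixed in advance. This is right, and it is why the remedy is a correction of wording. It does not make the 0.025 statement true.

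A narrower reading of 9.2.5 is also arguable. The co-primaries have their own sentence, and the 0.025 sentence follows one about key secondary endpoints, so 0.025 may never have been promised for the C6D1 trough. On that reading the 4.0% and 4.9% figures fall outside the stated claim. CT4W is still named in the list and still tested at 0.05, so the contradiction remains.

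The independence behind the 3.2% is not realistic. The two troughs come largely from the same participants, and VGPR responders are a subset of ORR responders. This objection stands against the precision of the figure, but allowing for correlated PK results makes the error larger.

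Finally, the protocol leaves technical detail to a SAP that is not at hand. That would answer an omission. Here the protocol makes a definite statement that its own rules contradict.

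**Conclusion.** The concern holds. As written, the procedure controls the familywise error at one-sided 0.05, not 0.025. The bound follows from the decision rules alone and needs no assumption about effect sizes or correlation. It is approached when a PK ratio sits at its margin and the other gating tests have power near 1. At planned power the error is 4.0% for the overall claim when the C6D1 ratio is at its margin, and about 3.2% to 3.8% when the CT4W ratio is. Those figures rest on the assumptions stated with them.

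The excess is confined to the two PK claims and the overall claim that depends on C6D1. The ORR, VGPR, infusion-reaction and satisfaction tests are not individually above 0.025, and for those four alone the sequence still bounds the familywise error at 0.025. This should be fixed, but it does not undermine the choice of PK criterion.

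**What to change.** Keep the 90% interval for both PK endpoints and correct 9.2.5, for example:

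> Non-inferiority on C6D1 C_trough and on CT4W is tested at one-sided 0.05 (lower limit of the two-sided 90% CI). ORR, VGPR or better rate, incidence of IRs and satisfaction are tested at one-sided 0.025. Over the whole sequence the familywise Type I error is bounded at one-sided 0.05; for the four non-PK hypotheses it is bounded at 0.025.

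This costs one change of wording, with no change to any test, margin or sample size.

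If the sponsor prefers to keep the 0.025 claim, both PK steps, not CT4W alone, must move to 95% intervals. That is a design change:

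- Co-primary PK power falls from 86% to about 78%, and the synopsis and 9.5 must say so.
- Joint co-primary power falls from 0.80 × 0.858 = 69% to 0.80 × 0.775 = 62% (independence assumed).
- Holding about 86% needs 166 evaluable per arm, or 2 × 166 / 0.5 = 664 randomized at 50% drop-out.
- CT4W power falls by at most 1.6 points at a CV of 42–50% with 133 per arm. At a CV of 75% it falls by about 8 points with 133 per arm and about 4 with 200. These CT4W numbers per arm are assumptions.

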9.2.6 Other/safety analysis

9.2.6.1 Adverse events

General common rules for adverse events

The AEs will be analyzed in the following 3 categories:

- Pre-treatment AEs: AEs that developed, worsened, or became serious during the pre-treatment period.
- TEAEs: AEs that developed, worsened, or became serious during the treatment-emergent period.
- Post-treatment AEs: AEs that developed, worsened, or became serious during the post-treatment period.

Similarly, the deaths will be analyzed in the pre-treatment, treatment-emergent and post-treatment periods.

Summaries will be provided for all grades combined and for Grade ≥ 3 (including Grade 5). Missing grades, if any, will be included in the “all grades” category.

Analysis of all adverse events

Adverse event incidence table will be provided by treatment group for all types of TEAEs: all TEAEs, all treatment emergent AESI (defined with a PT or a prespecified grouping), all treatment emergent SAEs and all TEAEs leading to permanent treatment discontinuation.

The AE summaries will be generated with number (and percentage) of participants experiencing at least one event.

Deaths will also be analyzed.

9.2.6.2 *Laboratory variables, vital signs, and electrocardiograms (ECGs)*

Quantitative analyses

For laboratory variables, vital signs and ECG variables, the following analyses will be applied for each planned visit on safety population.

Clinical laboratory values will be analyzed after conversion into standard international units. (International units will be used in all listings and tables).

Hematology and clinical chemistry results will be graded according to the NCI-CTCAE V5.0, when applicable. Number (and percentage) of participants with laboratory abnormalities (ie, all grades and by grade) using the worst grade during the treatment period will be provided for the safety population. Analyses will be performed according to PCSA.

For laboratory tests for which NCI-CTCAE v5.0 scale is not applicable, potentially clinically significant abnormality (PCSA) values are defined as abnormal values considered medically important by the Sponsor according to predefined criteria/thresholds based on literature review.

The PCSA criteria will determine which patients had at least 1 PCSA during the treatment period, taking into account all evaluations performed during the treatment-emergent period, including nonscheduled or repeated evaluations. The incidence of PCSA any time during the on-treatment period will be summarized by treatment group irrespective of the baseline level. For blood pressure/heart rate parameters, the incidence of PCSAs prior to study treatment administration at any cycle during the on-treatment period will be summarized by treatment group whatever the baseline level and/or according to the following baseline categories:

- Normal/missing.
- Abnormal according to PCSA criterion or criteria

The incidence of PCSAs during and after isatuximab administration at any cycle during the treatment period in the SC arm will also be summarized.

For laboratory variables graded by NCI-CTCAE. The number (and percentage) of participants with abnormal laboratory tests at baseline will be presented by grade.

The number (and percentage) of participants with abnormal laboratory tests during the treatment-emergent period will be summarized by grade. When appropriate, the number (and percentage) of participants with abnormality of any grade and with Grade 3-4 abnormalities will be provided.

For ECG, the incidence of participants with at least one abnormal ECG during the treatment-emergent period will be summarized regardless of the baseline level and according to the following baseline status categories:

- Normal/missing.
- Abnormal.

9.2.6.3 *Product complaints*

Product complaints will be summarized in the safety population.

9.2.7 Other analysis

For a regional or national emergency declared by a governmental agency, contingency measures are included in Appendix 9 ([Section 10.9](#)): Contingency measures for a regional or national emergency that is declared by a governmental agency.

9.3 INTERIM ANALYSES

No interim analysis with alpha spending is planned for this study.

9.4 TIMING OF PLANNED ANALYSIS

The cut-off date for the primary analysis is approximately 6 months after the LPI, which includes analysis on the primary endpoint and secondary endpoints when applicable. An update of PFS and OS will be performed approximately 15 months after LPI. The cut-off date for final OS analysis will be approximately 30 months after LPI.

9.5 SAMPLE SIZE DETERMINATION

A total sample size of 534 participants (randomization ratio 1:1, ie, 267 randomized participants in the SC arm, and 267 randomized participants in the IV arm) was determined to demonstrate non-inferiority of SC arm versus IV arm on the proportion ratio of participants who achieved ORR, and the geometric mean ratio of C_{trough} at steady state (corresponding to predose at C6D1). For the co-primary efficacy endpoint of ORR, the non-inferiority test for non-unity null according to Farrington and Manning (1990) was implemented. With 2.5% one sided Type I error rate, and a non-inferiority margin of 0.839 which was calculated as 40% retention of the observed historical clinical benefit of ORR ratio 0.7463 (upper bound of the 95% CI of rate ratio for Pd over CD38+Pd as demonstrated in ICARIA-MM trial) under the logarithm scale then converting back to its original scale, 534 randomized participants provide approximately 80% power for this

efficacy co-primary endpoint assuming that ORR for IV arm is 60.4% and the true response rate ratio is 1.02 for SC arm over IV arm. For the PK co-primary endpoint of C_{trough} at steady state, assuming C_{trough} at steady state follows log normal distribution with a true geometric mean ratio of 1 and a CV of 75%, and an assumed drop-out rate of no more than 50% to the PK per-protocol population, 534 randomized participants will provide at least an 86% power to show the lower bound of the 90% CI of the geometric mean ratio of C_{trough} at steady state is at least 80% (a non-inferiority margin of 80%).

Calculations were made based on SAS 9.4 ([1](#)).

10 SUPPORTING DOCUMENTATION AND OPERATIONAL CONSIDERATIONS

10.1 APPENDIX 1: REGULATORY, ETHICAL, AND STUDY OVERSIGHT CONSIDERATIONS

10.1.1 Regulatory and ethical considerations

- This study will be conducted in accordance with the protocol and with the following:
 - Consensus ethical principles derived from international guidelines including the Declaration of Helsinki and the applicable amendments and Council for International Organizations of Medical Sciences (CIOMS) International Ethical Guidelines.
 - Applicable ICH Good Clinical Practice (GCP) Guidelines.
 - The Regulation (EU) No 536/2014 of the European Parliament and the Council of 16 April 2014 on clinical trials on medicinal products for human use, as applicable.
 - The General Data Protection Regulation - (GDPR) and any other applicable data protection laws.
 - Any other applicable laws and regulations.
- The protocol, protocol amendments, ICF, IB, [IDFU] and other relevant documents (eg, advertisements) must be submitted to an IRB/IEC by the Investigator and reviewed and approved by the IRB/IEC before the study is initiated.
- Any amendments to the protocol will require IRB/IEC approval before implementation of changes made to the study design, except for changes necessary to eliminate an immediate hazard to study participants.
- Protocols and any substantial amendments to the protocol will require health authority approval prior to initiation except for changes necessary to eliminate an immediate hazard to study participants.
- The Investigator will be responsible for the following, as applicable:
 - Providing written summaries of the status of the study to the IRB/IEC annually or more frequently in accordance with the requirements, policies, and procedures established by the IRB/IEC.
 - Notifying the IRB/IEC of SAEs or other significant safety findings as required by IRB/IEC procedures.
 - Providing oversight of the conduct of the study at the site and adherence to requirements of 21 CFR, ICH guidelines, the IRB/IEC, Regulation No 536/2014 of the European Parliament and the Council of the European Union for clinical studies, European Medical Device Regulation 2017/745 for clinical device research, and all other applicable local regulations.

- Determining whether an incidental finding (as per Sanofi policy) should be returned to a participant and, if it meets the appropriate criteria, to ensure the finding is returned (an incidental finding is a previously undiagnosed medical condition that is discovered unintentionally and is unrelated to the aims of the study for which the tests are being performed). The following should be considered when determining the return of an incidental finding:
 - The return of such information to the study participant (and/or his/her designated healthcare professional, if so, designated by the participant) is consistent with all applicable national, state, or regional laws and regulations in the country where the study is being conducted, and,
 - The finding reveals a substantial risk of a serious health condition or has reproductive importance, AND has analytical validity, AND has clinical validity.
 - The participant in a clinical study has the right to opt out of being notified by the Investigator of such incidental findings. In the event that the participant has opted out of being notified and the finding has consequences for other individuals, eg, the finding relates to a communicable disease, Investigators should seek independent ethical advice before determining next steps.
 - In case the participant has decided to opt out, the Investigator must record in the site medical files that she/he does not want to know about such findings.
 - As applicable, according to requirements of the Regulation No536/2014 of the European Parliament and the Council of the European Union

The Sponsor will be responsible for obtaining approval from the Competent Authorities of the EU Member States and/or Ethics Committees, as appropriate, for any amendments to the clinical trial that are deemed as “substantial” (ie, changes which are likely to have a significant impact on the safety or physical or mental integrity of the clinical trial participants or on the scientific value of the trial) prior to their implementation.

According to the Regulation No 536/2014 of the European Parliament and the Council of the European Union and as specified by the applicable regulatory requirements in non-EU/EEA countries, Sanofi, as the clinical trial Sponsor, needs to report to the concerned regulatory agency/ies serious breaches without undue delay but not later than 7 calendar days of becoming aware of that breach. A serious breach is defined as a deviation of the version of the protocol applicable at the time of the breach or the applicable clinical trial regulation that is likely to affect to a significant degree the safety and rights of a subject or the reliability and robustness of the data generated in the clinical trial.

The Sponsor shall ensure that all parties involved in the conduct of the clinical trial promptly report any events that might meet the definition of a serious breach.

Therefore, Investigators shall within 48h after being aware of a deviation that might meet the definition of a serious breach, report to the Sponsor any suspected serious breach to enable the Sponsor to carry out the required assessment and notify the regulatory agency/ies in the event of a confirmed serious breach. To that extent, the principal Investigator must have a process in place to ensure that the site staff or service providers engaged by the principal

Investigator/institution are able to identify the occurrence of a (suspected) serious breach and that a (suspected) serious breach is promptly reported to the Sponsor through the contacts (e-mail address or telephone number) provided by the Sponsor.

